## Statistical Analysis Plan

Outcome metrics: vertical GRF impulse, anterior GRF impulse, peak-to-peak range of sagittal plane whole body angular momentum (WBAM), and peak-to-peak range of frontal plane WBAM.

Linear mixed effects regression was used to assess differences in biomechanical outcomes (the dependent variable) by foot type for each load by combining all loading conditions in a single model and using a foot type by load condition interaction to estimate means and mean differences in outcomes by foot for each load separately. This model assumes a common variance in outcomes across load and foot. Thus, standard errors for the means will be similar across load and foot. Subject and foot type within subject were considered random effects. Several random effects structures were considered (from subject ID intercept only to a full subject by foot interaction model) with the best model chosen based on likelihood ratio tests. Hypothesis testing for the overall association between outcome and foot type were carried out using conditional F-tests for each load type. For comparison, the Benjamini Hochberg (BH) adjustment was also applied to the F-tests for each model across the 5 load conditions to maintain a false discovery rate of 5%. Hypothesis testing for pairwise differences across feet was carried out using Tukey's method to account for the inflation of the Type 1 error due to assessment of 10 pairwise differences for each load. Analyses were carried out using R 4.2.3 (R Foundation for Statistical Computing, Vienna, Austria) and packages tidyverse, lme4, emmeans and lmerTest.

Outcome metrics: positive net ankle joint work.

Linear mixed-effects regression was used to assess differences in biomechanical outcome (i.e., prosthetic limb joint work over the entire gait cycle as dependent variable) by prosthetic foot for each load condition. All loads were combined in a single model with a foot-by-load interaction to estimate means and mean differences in outcome by foot within each load. The model assumed a common variance, yielding similar standard errors (SE) across loads and feet. Participant and foot within participant were included as random effects. Multiple random effects structures were compared using likelihood ratio tests to select the best-fitting model. The dependent variable was transformed when residual heteroscedasticity was detected. Hypothesis testing for the overall associations between foot and outcome variables were performed using conditional F-tests for each load. For comparison, the Benjamini-Hochberg correction was also applied across the loads to control the false discovery rate at 5%. Hypothesis testing for pairwise differences across feet was performed using Tukey method to account for the inflation of the Type-1 error due to multiple testing (10 comparisons per load). All analyses were conducted in R v4.2.3 (R Foundation for Statistical Computing, Vienna, Austria) using the following packages: tidyverse, lme4, emmeans, and lmerTest.

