5.6 Data Analysis

Kinematic and kinetic data from the experiment will be processed in Visual 3D (C-Motion Inc., Germantown, MD) and aggregated using custom project specific software (Matlab; Mathworks, Natick, MA). To determine changes in walking performance, we will calculate biomechanical quantities related to body support, forward propulsion and balance control including: the vertical ground reaction force (GRF) impulse, the anterior GRF impulse, and the peak-to-peak range of the frontal and sagittal whole-body angular momentum. We will also calculate mechanical energy expenditure (i.e., the sum of the joint mechanical work of each leg). The GRF and joint work metrics will be normalized by body weight and added load while whole-body angular momentum will be normalized by body weight and added load, walking speed and leg length.

Linear mixed-effects regressions will be used to detect differences in the biomechanical quantities (dependent variables) between study prostheses (independent variables) for each load condition separately (anterior, posterior, intact-side carry, and prosthetic-side carry) following an assessment of normality. This method allows inclusion of subjects who do not complete all study procedures (repeated measures analysis of variance (ANOVA) models do not). These analyses will test for differences between the study prostheses across the four different load carriage conditions with random effects for subject and subject by study prosthesis interaction. If the data is not normally distributed, we will consult with our biostatistician on an appropriate transform. An omnibus test for significance will be generated using a likelihood ratio test with an alpha level of 0.05. Individual pair-wise differences will be assessed using simultaneous inference and associated 95% confidence intervals. All statistical analyses will be performed by study staff using existing VA enterprise software (SPSS Statistics v22; IBM, Inc.). Exact p-values will be reported for each test.

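### The SAP's all-loads model lists no subject-by-load random effect, which costs power in every within-load foot comparison, and it states an unequal-variance check for only one of five outcomes

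*SAP*

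**What the plan says.** For the vertical and anterior GRF impulses and the sagittal and frontal angular-momentum ranges, the SAP puts all loads into one model with a foot-by-load interaction. It states: "This model assumes a common variance in outcomes across load and foot". It then draws the consequence: "Thus, standard errors for the means will be similar across load and foot". On random effects: "Several random effects structures were considered (from subject ID intercept only to a full subject by foot interaction model". The choice among them was made by likelihood ratio test. It gives no variance check or remedy for these four outcomes.

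For joint work, the second part of the SAP makes the same assumption ("The model assumed a common variance, yielding similar standard errors (SE) across loads and feet") but adds a response: "The dependent variable was transformed when residual heteroscedasticity was detected". It does not list the random-effects structures compared.

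Protocol Section 5.6 describes the regressions as separate for each load condition, "following an assessment of normality". Its transformation rule is triggered by non-normality, not by unequal spread: "If the data is not normally distributed, we will consult with our biostatistician on an appropriate transform". Neither document gives a standard deviation by foot.

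**The concern.** Prescription guidance will rest on the pairwise foot comparisons within each load, so their standard errors matter most. Combining the loads affects them in two ways.

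- **Subject-by-load variation.** Some people cope well with an anterior load and badly with a side carry, whichever foot they wear. In a model fitted to one load, the subject intercept absorbs this. In the combined model only a subject-by-load term can, and none is listed. Left in the residual, it widens the error bars of comparisons that it does not affect. Real differences among the wedge, the stiffer category and the dual keel foot could then be missed.
- **Variance by foot.** Four feet are passive and one is powered. If their variances differ, a pooled variance makes some pairs look too precise and others too imprecise. The SAP recognises unequal variance as a risk for joint work but states no check for the other four outcomes.

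**Working it through.** **The plan's own figures.** Protocol Section 5.6 gives power of 99% and 85% (H1, posterior and anterior load) and 98% and 99% (H2) for 20 subjects. A within-subject t test with zero correlation, 19 df and SE = SD × √(2/20) gives 99.3%, 85.5%, 98.6% and 99.9%, so the figures reproduce. They concern one unadjusted pair and do not depend on this point. They do place the effect size: difference/(SD × √2) is 27.0/(18.3 × √2) = 1.04, 16.1/(16.0 × √2) = 0.71, 1.8/(1.3 × √2) = 0.98 and 4.1/(2.4 × √2) = 1.21. The 0.82 used below is an assumption within that range.

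**Set-up (assumed).** Complete data, 5 feet × 5 loads, one value per cell, n=20, two-sided 5%. Subject-by-foot and residual variance are 0.5 each, so the remaining within-subject variance is 1.

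**Part 1: no subject-by-load term.** Let g be the subject-by-load variance.

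- True variance of a foot difference within one load: 2 × (0.5 + 0.5)/n = 2/n, because g cancels.
- The fitted model uses v = MS(subject-by-foot)/5 + 0.8 × MS(residual). In expectation MS(subject-by-foot) = 5 × 0.5 + 0.5 = 3.0 and MS(residual) = 0.5 + g.
- So v = 0.6 + 0.8 × (0.5 + g) = 1 + 0.8g, and model SE/true SE = √(1 + 0.8g).
- Approximate Tukey power, critical value 2.79: Φ(0.82 × √20 − 2.79 × SE ratio), with 0.82 × √20 = 3.67.

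| g | SE ratio | Power, approximation | Power, simulation |
|---|---|---|---|
| 0 | 1.00 | 81% | 82% |
| 0.25 | √1.2 = 1.095 | 73% | 74% |
| 0.50 | √1.4 = 1.183 | 64% | 65% |

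Adding the term restores about 82%. At n=40, the figure in Protocol Section 3.0, 0.82 × √40 = 5.19 and the approximation gives 99%, 98% and 97%. The loss is therefore material near n=20 and slight at n=40.

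**Part 2: variance differing by foot.** Let r be the powered-foot SD divided by the passive-foot SD (not in the documents, so shown as a range). Under subject and subject-by-foot intercepts, the pooled variance is p = (4 + r²)/5. Model SE/true SE is √(2p/(1 + r²)) for powered versus passive and √p for passive versus passive.

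| r | p | Powered vs passive | Passive vs passive |
|---|---|---|---|
| 0.5 | 0.85 | 1.17 | 0.92 |
| 1 | 1.00 | 1.00 | 1.00 |
| 1.5 | 1.25 | 0.88 | 1.12 |
| 2 | 1.60 | 0.80 | 1.26 |

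If an unstructured subject-by-foot covariance is selected, only the residual (share f = 0.5) is pooled. At r=2:

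- Powered versus passive: √[(0.5 × 5 + 0.5 × 5/5 + 1.6 × 0.5 × 1.6)/5] = √(4.28/5) = 0.93.
- Passive versus passive: √[(0.5 × 2 + 0.5 × 2/5 + 1.28)/2] = √(2.48/2) = 1.11.

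Null simulation at n=20 (6,000 runs, simple structure): Tukey familywise error per load is 5.1% at r=1, 5.5% at 1.5 and 7.0% at 2. Unadjusted error for a single pair, powered versus passive and then passive versus passive, is 8.5% and 3.0% at r=1.5, and 11.7% and 1.4% at r=2. At n=40 and r=2 it is 12.2% and 1.3%, so more subjects do not cure it.

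**The case against.** A common residual variance is the ordinary mixed-model default, and the SAP discloses it. Four further points have force.

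- **The powered foot's variance is unknown.** A reader might infer that powered-foot comparisons look too precise. The documents do not support this: no SD by foot is given, the direction reverses if that foot is less variable, and nothing is wrong if variances are equal.
- **The SAP does not strictly force one variance.** A full subject-by-foot model may let between-subject variance differ by foot. In simulation a likelihood ratio test preferred that form in 31% of trials at r=1.5 and 70% at r=2, and the distortion is then smaller. The SAP's expectation of similar standard errors suggests the simpler form, but the text does not settle it.
- **Silence is not proof.** That no check is stated for four outcomes does not show that none was made.
- **Omitting subject-by-load is conservative.** It cannot inflate false positives, and its size is assumed.

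A robust analysis also has a price. At 19 df the Tukey critical value is 3.01 instead of 2.79, and power at 0.82 is about 74% even with correct standard errors: Φ(3.67 − 3.01). That argues against making it primary throughout. What survives is the missing subject-by-load term, which is nearly free to add, and the uneven treatment of variance checks.

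**Conclusion.** The point holds in two parts of different strength.

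The missing subject-by-load term is the firmer one. Any such variation makes standard errors for within-load foot comparisons too large: by about 9% or 18% at n=20 if it is 25% or 50% of the remaining within-subject variance. Tukey power then falls from about 82% to 74% or 65% at a standardised difference of 0.82. The mechanism follows from the model as written. The shares and effect size are assumptions, and the loss is only a point or two at n=40.

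The variance-by-foot part is a gap in checking, not a demonstrated bias. Individual pairs could be distorted in either direction. Familywise error rises only to about 5.5% to 7% for SD ratios of 1.5 to 2 under the simple structure. The documents do not support a claim that the evidence on the powered foot is overstated, or that the trial's conclusions are invalid.

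**What to change.** 1. Add a subject-by-load random intercept to the candidate structures for all five outcomes. lme4, already listed in the SAP, can fit it.
2. Apply the residual heteroscedasticity check stated for joint work to all five outcomes. Report the selected random-effects structure and the residual variance by foot for each.
3. Give a sensitivity analysis with foot-specific residual variance (for example nlme with varIdent) or small-sample cluster-robust (CR2) standard errors by participant. Make it primary only where the check shows unequal variance.

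Cost: some added wording, one extra R package for the third item, and fewer degrees of freedom for the robust version. The SAP is written in the past tense, so models already fitted may have to be re-run. No new data are needed.

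### The pooled five-load model names no subject-by-load random effect and the SAP does not state the row unit, so the standard errors of within-load foot comparisons may be wrong, in a direction the documents do not settle

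*SAP*

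**What the plan says.** The SAP has two analysis descriptions. The first covers the two ground reaction force impulses and the two whole-body angular momentum ranges; the second covers ankle joint work.

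- **Pooling.** The first describes "combining all loading conditions in a single model and using a foot type by load condition interaction", with feet then compared within each load by F-test and Tukey contrasts. The second does the same for joint work. Both assume one common residual variance.
- **Random effects.** The first names subject and foot within subject, and describes the candidates thus: "Several random effects structures were considered (from subject ID intercept only to a full subject by foot interaction model". The second says "Participant and foot within participant were included as random effects" and "Multiple random effects structures were compared using likelihood ratio tests to select the best-fitting model", without listing the candidates.
- **Protocol, Section 5.6.** The analysis there compares outcomes "between study prostheses (independent variables) for each load condition separately", "with random effects for subject and subject by study prosthesis interaction".
- **Row unit.** Neither document states it. Section 5.5 gives one one-minute walk per foot and load. Section 5.6 says the data are "aggregated using custom project specific software", which could mean cell averages. A subject-by-prosthesis effect in a separate fit for each load, however, would need several rows per cell.

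**The concern.** People differ in how their gait changes under a front, back or side load. For one person under one load, that response is common to all five feet, so it drops out of any comparison of feet within the load. A separate fit per load absorbs it in the subject intercept. Once the loads are pooled, it needs its own variance term. Without one it goes into the residual and from there into the standard error of every within-load foot difference.

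The study's aim is to identify the best foot under each load, so these contrasts are its central result. A wrong standard error can hide a real difference or, under other conditions, suggest one that is not there.

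**Working it through.** **Plan's own figures.** The only power figures are in Protocol Section 5.6, for n=20: 99% and 85% (vertical impulse, posterior and anterior load) and 98% and 99% (anterior impulse, same loads). A paired t-test with 19 df and SD of the difference = SD × √2 gives 99.3, 85.5, 98.6 and 99.9%. They reproduce and are not in dispute.

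**Inputs.** There are five loads (SAP) and five feet (10 pairs = 5×4/2, SAP), with n=20 (Protocol power analysis). The variance components are not in the documents. Assumed: cell error e=1, subject-by-foot f=0.25 or 1, subject-by-load l=0.1, 0.25 or 0.5.

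**1. Averaged rows, equal error variance, foot-within-subject fitted.** Expected mean squares:

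- subject×foot: e+5f, on 19×4=76 df
- subject×load: e+5l, on 76 df
- subject×foot×load: e, on 19×16=304 df

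Without a subject-by-load term, the last two pool into a residual R on 380 df, with expectation [76(e+5l)+304e]/380 = e+l. Omitting the common factor 2/n, the fitted variance of a within-load foot difference is (MS_SF+4R)/5, with expectation f+e+0.8l. The true value is f+e. The SE ratio is therefore √(1+0.8l/(f+e)), whatever n is. For example, at f=0.25 and l=0.5 it is √(1+0.4/1.25) = 1.149.

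| | l=0.1 | l=0.25 | l=0.5 |
|---|---|---|---|
| SE ratio, f=0.25 | 1.032 | 1.077 | 1.149 |
| SE ratio, f=1 | 1.020 | 1.049 | 1.095 |
| Null F rejection, f=0.25 | 3.8% | 2.7% | 1.5% |
| Null F rejection, f=1 | 4.3% | 3.4% | 2.3% |
| Power of a Tukey contrast that has 80% with the term, f=0.25 | 78% | 74% | 67% |
| Same, f=1 | 78% | 76% | 72% |

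Rejection and power come from simulated mean squares with Satterthwaite df. A separate simulation at f=0.25 gave 3.9, 2.6 and 1.4%. With the subject-by-load term, or with per-load fits, rejection returns to about 5%. At l=0 the ratio is 1.

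**2. Intercept-only structure selected.** The residual expectation is e+(5/6)(f+l), so SEs are too large only when l>0.2f. At l=0, 0.1, 0.25 and 0.5 the ratios are 0.98, 1.02, 1.06 and 1.14 (f=0.25), or 0.96, 0.98, 1.01 and 1.06 (f=1).

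**3. Error variance differs by load.** Let load k have error e_k and let the average be e. The fitted variance is still f+e+0.8l, but the true one at load k is f+e_k. The test is conservative there only if e_k−e < 0.8l. With f=0.25 and average e=1:

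| l, e_k | SE ratio, SAP model | Null F, SAP model | Null F, subject-by-load added |
|---|---|---|---|
| 0.1, 1.2 | √(1.33/1.45)=0.96 | 6.9% | 8.5% |
| 0.25, 1.4 | √(1.45/1.65)=0.94 | 8.1% | 12.7% |

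Per-load fits stay near 5% in both settings, because each uses its own mean square, with expectation f+e_k.

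**4. Stride rows.** With m strides per cell and s3 the subject-by-foot-by-load part of the cell error e, put w=(e−s3)m. Then R=[76m(e+5l)+304me+500(m−1)w]/[380+500(m−1)], and the fitted variance is f+e/5+0.8R/m. For m=20 to 50 and l=0 to 1:

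- s3=0: ratio 1.00 to 1.01
- s3 at 5% of cell error: 0.98 to 1.00
- s3 at 20 to 80%: 0.70 to 0.95 (null F 7 to 31%) at f=0.25, and 0.83 to 0.97 (6 to 16%) at f=1

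In the 20 to 80% range, adding subject-by-load alone leaves 0.70 to 0.94 and 0.83 to 0.96.

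**The case against.** **Size.** The documents give no value for l, f or e, and l may be small: "The GRF and joint work metrics will be normalized by body weight and added load". On the protocol's own effects, the largest inflation above (15%) moves power only from 99.3 to 98.3%, 98.6 to 96.9% and 99.9 to 99.8%. Only the anterior-load vertical impulse moves materially, from 85.5 to 77.4%, and at 3% inflation it loses about 1.5 points. This stands: the percentages illustrate a range and are not estimates for this trial. Those checks make no Tukey adjustment, so they do not show that the loss is negligible for the planned contrasts.

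**Silence.** The joint-work description lists no candidates, so a load term may have been among them. This stands too, although the random effects it says were included contain none.

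**Direction.** A reader might infer that the tests are simply conservative and cannot add false positives. The documents do not support that. It needs averaged rows and equal error variance across loads; the first is not stated, and the second is only a model assumption. The joint-work description itself provides for a transformation when residuals are heteroscedastic.

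**Remedy.** A reader might also infer that adding a subject-by-load term is always safe. Step 3 shows that it raises the error rate at a load whose error variance is above average.

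**Conclusion.** The point holds in conditional form. No subject-by-load random effect is named in either SAP description, and pooling removed the protection that the protocol's separate fits would have given. With averaged rows, equal error variance across loads, foot-within-subject fitted and l>0, within-load SEs are too large by √(1+0.8l/(f+e)): about 2 to 15% over the assumed range, with null F rejection of about 1.4 to 4.3%. A contrast that would have 80% power loses about 2 to 13 points.

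Outside those conditions the result changes. At l=0 nothing is wrong. If e_k exceeds the average error variance by more than 0.8l, the tests at that load are anti-conservative. With stride rows the missing term itself matters by about 1% or less, but an unmodelled subject-by-foot-by-load component makes SEs too small. Until the row unit is stated, a reader cannot tell which case applies.

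**What to change.** State the row unit, and average to one value per subject, foot and load.

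**Preferred.** Fit each load separately with foot as a fixed effect and `(1|subject)`. This is close to Protocol Section 5.6 and removes both the subject-by-load and the unequal-variance problems. It costs about 2 points of power (78% against 80%). It drops the subject-by-prosthesis term, which cannot be separated from error with one row per cell.

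**If the pooled model is kept.** Use `foot*load + (1|subject) + (1|subject:foot) + (1|subject:load)` together with load-specific residual variances, or at least a check of equal variance across loads. Confirm that the listed R packages can fit this. Include the subject-by-load term outright: at n=20 with equal variances, a likelihood ratio test would select it in about 62% of datasets at l=0.1 (99% at 0.25, 100% at 0.5, 2% at l=0). With equal variances, including it at l=0 costs no power. Zero variance estimates will sometimes occur.

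**If stride rows are kept.** Also add `(1|subject:foot:load)`.

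The F-test, Tukey and Benjamini-Hochberg steps can stay. The SAP is written in the past tense; if results exist, report the refit beside them, whichever way it goes.

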The aim of this research is to create guidance for VA clinicians who prescribe prostheses to veterans with a lower limb amputation who frequently carry infants, toddlers or other loads. To achieve this aim, we will conduct a human subject experiment with help of twenty individuals with below-knee amputations. Study participants will walk on a treadmill with no added load and four added load conditions using a weighted pack (13.6 kg or ~30 lbs) to simulate an infant, toddler, or other load. The four conditions include the pack strapped to their front, their back, and carried with their arms on the intact limb side and the prosthetic limb side. Each participant will wear a usual prosthetic foot, this same foot with a heel-stiffening wedge, the same prosthetic foot but one category stiffness higher, a new-to-market dual keel prosthetic foot intended for load carrying situations, and a powered ankle foot prosthesis. We will analyze the results of this experiment to determine which prosthetic foot (if any) and which load carrying condition (if any) is most advantageous.

List of Abbreviations

AE – adverse event
ANOVA – analysis of variance
ASIS - anterior superior iliac spine
CCTV - closed circuit television
CO - Colorado
CRQ – continuing review questionnaire
d – Cohen's *d* statistic
EMG – electromyography
GAS - medial gastrocnemius
GMAS - gluteus maximus
GMED - gluteus medius
GRF – ground reaction force
H – hypothesis
HAM - biceps femoris long head
HIPAA – health insurance portability and accountability act
IRB – institutional review board
ISO - Information Security Officer
Kg - kilograms
Lbs - pounds
M - Million
MA – Massachusetts
MD – Maryland
MIRB – Minneapolis Institutional Review Board
N - number of individuals
PHI – personal health identifiers
PI – principal investigator
PO – privacy officer
RF - rectus femoris
ROP – report of other problem
SA – specific aim
SAE – serious adverse event
SOL – soleus
SSWS - self-selected walking speed
TA - tibialis anterior
UW – University of Washington
VA – Veterans Affairs
VAPSHCS – Veterans Affairs Puget Sound Health Care System
VAS - vastus medialis
WA - Washington

Contents

Protocol Title: Load Carriage by Individuals with Lower Limb Amputation.....	5
1.0 Study Personnel.....	5
2.0 Introduction.....	5
3.0 Objectives.....	7
4.0 Resources and Personnel.....	8
5.0 Study Procedures.....	8
5.1 Study Design.....	8
5.2 Recruitment Methods.....	9
5.3 Informed Consent Procedures.....	12

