3.0 Objectives

The purpose of this research is to provide prosthesis prescription guidance for VA clinicians whose patients carry infants, toddlers, and other loads.

The specific aim of this research is to identify the study prosthetic foot that minimizes biomechanical gait deviations when compared to the standard-of-care for veterans with lower limb amputation who carry infants, toddlers, or other loads.

We will conduct a human subject experiment with unilateral transtibial amputees (n=40). Each participant will walk on an instrumented treadmill with no added load and four added load conditions of 13.6 kg: anterior, posterior, intact-side carry, and prosthetic-side carry. Using a

within-subject experimental design with block randomization, each participant will wear: a standard-of-care prosthetic foot, this same prosthetic foot with a heel-stiffening wedge, this same prosthetic foot but one category stiffer, a dual keel prosthetic foot intended for load carriage applications, and a powered ankle-foot purported to adapt to changing loads.

In general, we hypothesize that one of these prosthetic feet will minimize biomechanical deviations for (1) no added load, (2) anterior added load, (3) posterior added load, (4) intact-side carry load, and (5) prosthetic-side carry load.

Our specific hypotheses for each load condition are:

H1 a study prosthesis exists that maximizes the vertical GRF impulse (a measure of body support),

H2 a study prosthesis exists that maximizes the anterior GRF impulse (a measure of body forward propulsion),

H3 a study prosthesis exists that minimizes the peak-to-peak range of sagittal plane whole-body angular momentum (a measure of balance control primarily for anterior and posterior added load conditions),

H4 a study prosthesis exists that minimizes the peak-to-peak range of frontal plane whole-body angular momentum (a measure of balance control primarily for intact-side and prosthetic-side added load conditions), and

H5 a study prosthesis exists that minimizes the mechanical energy expenditure (allow for more efficient locomotion).

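### The SAP gives no rule for deciding H1–H5: the F-test cannot show that a best foot exists, and winning all four Tukey comparisons is valid but conservative next to Hsu's comparison with the best

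*SAP*

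**What the plan says.** The questions are in the protocol. The synopsis sets out to "determine which prosthetic foot (if any) and which load carrying condition (if any) is most advantageous". In Section 3.0 (Objectives) the specific aim is to "identify the study prosthetic foot that minimizes biomechanical gait deviations when compared to the standard-of-care". H1 states, for each load, that "a study prosthesis exists that maximizes the vertical GRF impulse"; H2–H5 have the same form, with maximizes or minimizes as the outcome requires.

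The tests are in the SAP. For the ground reaction force and angular momentum outcomes: "Hypothesis testing for the overall association between outcome and foot type were carried out using conditional F-tests for each load type". Then "Hypothesis testing for pairwise differences across feet was carried out using Tukey's method", in order to "account for the inflation of the Type 1 error due to assessment of 10 pairwise differences for each load". Ten pairs means five feet. The joint-work block repeats the scheme: "Hypothesis testing for pairwise differences across feet was performed using Tukey method". Protocol Section 5.6 has the same shape: "An omnibus test for significance will be generated using a likelihood ratio test with an alpha level of 0.05", followed by simultaneous pairwise inference with 95% confidence intervals.

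Neither document says what result would confirm H1–H5, gives a rule for calling a foot best, or names the standard-of-care foot as the reference in the testing.

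**The concern.** The hypotheses claim that one foot comes out on top. The alternative of the F-test is only that the feet are not all equal, which is also true when one foot is poor and the other four are tied. Because no decision rule is given, a reader of the results could apply either of two rules, and they behave very differently:

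- Taking a significant F as support for H1–H5 would often endorse a best foot that does not exist.
- Taking four Tukey wins as the rule is safe, but it can miss a foot that really is best.

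The stated purpose is prescription guidance, so the choice between these rules decides whether a foot is recommended for a given load.

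**Working it through.** **Inputs.** Protocol Section 5.6 gives four differences with SDs (N*s/kg), and a power for one unadjusted pair at p<0.05 with 20 subjects:

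- H1 posterior: 27.0, SD 18.3, power 99%
- H1 anterior: 16.1, SD 16.0, power 85%
- H2 posterior: 1.8, SD 1.3, power 98%
- H2 anterior: 4.1, SD 2.4, power 99%

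The synopsis and the power text use n=20; Section 3.0 says n=40. Five feet follow from the SAP's ten pairs.

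**Step 1: reproduce the plan's power.** Paired t-test, 19 df, two-sided 0.05, with SD of the difference = SD × √2 (zero within-subject correlation). For H1 anterior, 16.1 / (16.0 × 1.414) = 0.7115. Noncentrality = 0.7115 × √20 = 3.18, and power = 85.5% (stated: 85%). The other three come to 99.3%, 98.6% and 99.9%, in line with the stated 99%, 98% and 99%. For H1 anterior, taking 16.0 as the SD of the difference itself would give 98.9%, so the √2 reading is the one that fits.

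**Step 2: critical values of |t|.** Five feet, df = (20 − 1) × (5 − 1) = 76.

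- Unadjusted: 1.992
- Tukey, 10 pairs: 2.794
- Dunnett, two-sided, 4 contrasts: 2.49
- One-sided Dunnett, which is the Hsu criterion: about 2.20

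**Step 3: what a significant F shows.** Simulation at n=20 and 0.71 SD of the paired difference:

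| True pattern | F significant | Tukey names a single best | Hsu names a single best |
|---|---|---|---|
| One foot best, four equal | 90% | 36% | 62% |
| Two feet tied for best | 98% | under 1% (false) | about 3% (false) |
| Four tied, one worse | about 90% | under 0.1% (false) | about 0.3% (false) |

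Tukey names a foot when its lead over the runner-up exceeds 2.794 standard errors of a difference. Hsu names it when the lead exceeds about 2.20. In the last two rows no single best foot exists, yet F is nearly always significant.

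**Step 4: where the gain comes from.** With the two-sided Dunnett value (2.49) in place of Hsu's, the first row gives 49%. So 49 − 36 = 13 points come from not paying for all ten pairs, and 62 − 49 = 13 points from the one-sided criterion.

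**Step 5: other stated effects and n=40.** Chance of naming a truly best foot that leads four equal feet:

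| Effect | n | Tukey | Hsu |
|---|---|---|---|
| H1 anterior | 20 | 36% | 62% |
| H1 posterior | 20 | 90% | 97% |
| H2 posterior | 20 | 84% | 95% |
| H2 anterior | 20 | 98% | almost 100% |
| H1 anterior | 40 | 88% | 97% |

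**Step 6: one foot against standard-of-care.** Noncentral t with the Step 2 critical values. For H1 anterior at n=20, Tukey gives 65% and Dunnett 75%. For the other three effects the figures are 96.7% and 98.4%, 94.0% and 96.8%, and 99.5% and 99.8%, so under 3 points. For H1 anterior at n=40 they are 95.8% and 97.8%.

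**The case against.** Two stronger readings are tempting, and the documents support neither.

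- **That the plan answers neither of its questions.** The four contrasts with standard-of-care are among the ten Tukey pairs, with type I error controlled. A foot that beats all four others under Tukey is validly the best. Both questions are answered, conservatively.
- **That the SAP lets a significant F stand for a best foot.** It describes the F-test as a test of overall association and follows it with pairwise comparisons, and the synopsis allows that no foot may be best. The 90% in the one-worse-foot pattern is therefore not a false-positive rate of the plan. It is the power of F to detect a real difference, and it becomes an error only if someone reads F as confirming H1–H5.

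The case for all pairs is also good. Protocol Section 2.0 presents the stiffer foot, heel wedge, dual keel and powered ankle as competing options, so pairs without the standard-of-care foot can inform prescribing. That is a reason to keep Tukey and to make Dunnett optional.

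Finally, 36% against 62% is the worst of the four stated effects, at the smaller of the two sample sizes, and half of the gain comes from sidedness. Tukey is also the stricter guard against a false best foot (under 1% against about 3% when two feet tie). All of this stands. What remains is that neither document says how H1–H5 are to be decided.

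**Conclusion.** The concern holds as a missing decision rule with a more powerful method available; it is not an invalid analysis. F alone cannot support H1–H5. Four Tukey wins can, but at n=20 on the H1 anterior inputs they find a truly best foot about one time in three, against 62% with Hsu's method. For the other stated effects, and for H1 anterior at n=40, the difference is at most 11 points (84% against 95%).

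The figures assume five feet, complete data, equal variances and correlations across feet, 76 error df at n=20 for a single load, and zero within-subject correlation, which is the reading that reproduces the stated 85%. The H1 pilot inputs come from one subject, so the absolute power figures are fragile. The ordering of the critical values, and the logic that a significant F does not imply a best foot, do not depend on those inputs.

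**What to change.** On the same fitted model, for each outcome and load:

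1. Decide H1–H5 by Hsu's multiple comparisons with the best. Call a foot best only if its simultaneous interval against the best of the others excludes zero. Otherwise report the set of feet not shown to be inferior.
2. State that a significant F-test alone does not support H1–H5.
3. Keep Tukey for the pairwise estimates and intervals.
4. Optionally, name standard-of-care as the reference for the specific aim and add Dunnett contrasts, stating which family is primary. The gain is 10 points for H1 anterior at n=20 and 2 to 3 points or less elsewhere.

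The cost is a few sentences in the SAP and a few lines of code on the estimated means already produced. The downside is one more reported procedure, with a one-sided criterion that should be stated openly. The SAP is written in the past tense, so any re-analysis should be labelled post hoc.
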